3.13.8 Consecutive absence seizure freedom based on EEG

The endpoint of consecutive absence seizure freedom based on EEG is defined per 6-month period as having no absence seizures on scheduled or unscheduled EEGs during that period.

The endpoint of cumulative consecutive absence seizure freedom based on EEG is defined per 6-month period as having no absence seizures on scheduled or unscheduled EEGs during that period and all preceding periods.

Consecutive absence seizure freedom based on 1-hour EEG will be assessed at each FEV, YEV, and FV, as applicable, individually and cumulatively at each visit, truncated at the Month 24 YEV (for participants who reach Month 24). The derivation will be the same as that outlined in [Section 3.13.2](#), except without the consideration of concomitant AEDs or benzodiazepines usage. In addition, for this analysis, unscheduled EEGs and EEGs performed at the EDV that were not mapped to a scheduled visit will be considered.

In each 6-month period, a study participant is defined as absence seizure free if they meet all the following criteria:

1. At least one 1-hour EEG (either scheduled or unscheduled) was conducted on the study participant at any time up to and including the scheduled FEV or YEV at the end of the 6-month period
2. Quality of at least one 1-hour EEG while awake deemed sufficient for analysis
3. No absence seizure identified while awake on any 1-hour EEG (scheduled and unscheduled) performed within the specified period

Specific algorithmic rules for each of the above criteria are defined as follows:

Criterion 1: A study participant is defined as receiving the 1-hour EEG if there is a record in the eCRF that at least one 1-hour EEG was conducted (either scheduled or unscheduled) within the 6-month period.

Criterion 2: The EEG is deemed of sufficient quality if at least 30 minutes of readable EEG while awake is recorded for at least one 1-hour EEG during the specified 6-month period. Note that if a participant has more than one 1-hour EEG during a 6-month period, it is only necessary to meet this criterion for one of these assessments.

Criterion 3: 1-hour EEG with no absence seizures recorded on the EEG eCRF (ILAE code IIA). Note that Criterion 3 must be met for all EEGs performed within the specified 6-month period regardless of whether each of these EEGs fulfils Criterion 2.

Note that Criterion 2 and 3 can only be assessed if Criterion 1 is met.

In each 6-month period, if the study participant does not meet all the criteria for absence seizure freedom they will be regarded as not absence seizure free.

In the event of an unscheduled EEG or an EEG performed at an EDV or FV that has not been mapped to a scheduled visit, if this EEG is on the same day as a scheduled visit this will be attributed in the analysis to the 6-month period of the scheduled visit. Otherwise, if this is not on the same day as a scheduled visit, this will be attributed in the analysis to the 6-month period of the following scheduled visit. For example, if an unscheduled EEG is performed between the Month 6 FEV and the Month 12 YEV, this will be considered in the analysis for the Month 12 YEV. As a further example, if an unscheduled EEG is performed on the same day as the Month 24 YEV, this will be considered in the analysis for the Month 24 YEV.

In the event of a missed scheduled visit any unscheduled EEG will be attributed to the period of time between the preceding visit and the next planned scheduled assessment visit relative to the EV, as defined in [Table 3-5](#). For example, if an unscheduled EEG is performed after the Month 9 MEV and the scheduled Month 12 YEV is missing, then the unscheduled Month 9 assessment will be considered in the analysis for the period from the day after the Month 6 FEV up to and including Day 365 (Protocol scheduled assessment day for Month 12 YEV).

If a participant discontinues early, their EEG performed at the EDV will be attributed to the 6-month periods of time following the preceding visit. For example, if an EDV is performed at Month 9 MEV, then the EDV assessment will be considered in the analyses for the periods from the day after the Month 6 FEV up to and including Day 365 (Protocol scheduled assessment day for Month 12 YEV). All subsequent 6-month periods for the participant will be regarded as not absence seizure free.

If a participant has a FV prior to the scheduled Month 24 YEV, their EEG performed at the FV will be attributed to the 6-month period of time following the preceding visit. For example, if a FV is performed at Month 9 MEV, then the FV assessment will be considered in the analyses for the period from the day after the Month 6 FEV up to and including Day 365 (Protocol scheduled assessment day for Month 12 YEV). The participant will not be included in the analyses for all subsequent 6-month periods.

If a participant is regarded as absence seizure free at the scheduled FEV or YEV assessment (or at EDV) and absence seizure free at all unscheduled assessments since the last scheduled FEV or YEV assessment, then they will be regarded as absence seizure free in that 6-month period in the

consecutive analysis. If a participant is regarded as not absence seizure free at the scheduled FEV or YEV assessment (or at EDV) or at any unscheduled assessments since the last scheduled FEV or YEV visit, then they will be regarded as not absence seizure free for that 6-month period.

For the cumulative consecutive absence seizure freedom analysis, a study participant will be categorized as absence seizure free until the 6-month period in which they are first classified as not absence seizure free. After the recurrence of absence seizures, the participant is classified as not absence seizure free regardless of whether they met the criteria for absence seizure freedom in subsequent 6-month periods.

If a participant discontinues early, all subsequent 6-month periods for the participant are considered as not absence seizure free, regardless of their cumulative absence seizure status at the time of the EDV.

If a participant performs a FV prior to the Month 24 YEV and becomes not absence seizure free at any point prior to the FV then the participant will remain in the analyses for subsequent 6-month periods as not absence seizure free. However, if the participant performs a FV prior to the Month 24 YEV and they remain absence seizure free until the FV then they will remain in the analyses until the period of the FV, and will be excluded from the analyses for all subsequent 6-month periods.

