If a study participant discontinues the study during a relevant period then Criterion 1 will be checked and if met, the participant will be assessed for absence seizure freedom in the period of discontinuation. If Criterion 1 is not met, then the status will be imputed as not absence seizure free for that specific period and for all subsequent 6-month periods (where applicable), ending at Months 19 to 24.

If a study participant has a FV during a relevant period then Criterion 1 will be checked and if met, the participant will be assessed for absence seizure freedom in the period of the FV. If Criterion 1 is not met, then the participant will not be included in the analyses for that specific period and for all subsequent 6-month periods (where applicable), ending at Months 19-24.

For the cumulative consecutive absence seizure freedom analysis, a study participant will be categorized as absence seizure free until the 6-month period in which they are first classified as not absence seizure free. After the recurrence of absence seizures, the participant is classified as not absence seizure free regardless of whether they met the criteria for absence seizure freedom in subsequent 6-month periods.

If a participant discontinues early, all subsequent 6-month periods for the participant are considered as not absence seizure free, regardless of their cumulative absence seizure status at the time of the EDV.

If a participant performs a FV before the end of the Month 19-24 period and becomes not absence seizure free at any point prior to or at the FV then the participant will remain in the analyses for subsequent 6-month periods as not absence seizure free. However, if the participant performs a FV before the end of the Month 19-24 period, and they remain absence seizure free until the FV, then they will remain in the analyses until the period of the FV if they met Criterion 1 during the period of the FV, or the period prior if they did not meet Criterion 1 during the period of the FV, and will be excluded from the analyses for all subsequent 6-month periods.

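### Cumulative 6-month seizure freedom drops participants still free at an early Final Visit instead of censoring them, and the stated Safety Set denominator conflicts with that exclusion; later-period values are biased downward

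*SAP*

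**What the plan says.** An FV can come before Month 24. Participants who move to another BRV study, an access program or commercial BRV complete an FV rather than an Early Discontinuation Visit (EDV) (protocol 4.1; SAP 2.3.1), and SAP 3.3.5 counts them as completers.

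The cumulative rules then depend on status at the FV:

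- **EEG (SAP 3.13.8), already failed:** a participant who "becomes not absence seizure free at any point prior to the FV then the participant will remain in the analyses for subsequent 6-month periods" is counted in them as not free.
- **EEG, still free:** "they will remain in the analyses until the period of the FV, and will be excluded from the analyses for all subsequent 6-month periods".
- **Diary (SAP 3.13.9), already failed:** a participant who "becomes not absence seizure free at any point prior to or at the FV then the participant will remain in the analyses".
- **Diary, still free:** kept up to the last period with adequate diary completion, "and will be excluded from the analyses for all subsequent 6-month periods".

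Two neighbouring rules help in reading these. In the non-cumulative EEG analysis, an early FV removes the participant whatever the status: "The participant will not be included in the analyses for all subsequent 6-month periods". After an early discontinuation, "all subsequent 6-month periods for the participant are considered as not absence seizure free, regardless of their cumulative absence seizure status".

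SAP 8.1.5 and 8.1.6 state that, in every summary, the free and not-free percentages are taken over the number of participants in the SS. SAP 8.1.7 contains the only prespecified efficacy sensitivity analyses, and they vary only the diary-completion threshold.

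**The concern.** An FV caused by transfer to another source of BRV is, on its face, administrative censoring: follow-up ends and later status is unknown. Under the cumulative rule, people who leave while free stop contributing to the numerator at later periods, although some of them would have stayed free. Nothing puts that contribution back.

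The SAP also does not say what happens to these people in the denominator. Sections 3.13.8 and 3.13.9 exclude them; sections 8.1.5 and 8.1.6 divide by the whole SS. The two readings give different results.

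At stake is the period-by-period account of sustained seizure freedom in the later periods. It would depend partly on how many participants transfer early rather than on how they did on the drug. The study is single-arm and descriptive, so the reported percentage is itself the result.

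**Working it through.** The plan gives no figure to reproduce: there is no sample size calculation, no expected seizure-free rate and no expected number of early FVs.

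**Inputs.** N = 140 (protocol 9.8, approximate enrolment, used only for scale). All other inputs are assumptions: a share q = 0.80 of those still free stays free in each 6-month period; a share c has an FV in period 2, unrelated to outcome; nobody discontinues early. Let S(k) = q^k, so S(2) = 0.64 and S(4) = 0.4096. The true Month 24 value is 41.0%.

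**At c = 20%**

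- Early FVs: 0.20 × 140 = 28. Free at the FV and later removed: 28 × 0.64 = 17.9. Failed and kept: 28 × 0.36 = 10.1.
- Followed to Month 24: 112, of whom 112 × 0.4096 = 45.9 are cumulatively free.
- Reading A (excluded participants leave the denominator): 45.9/(112 + 10.1) = 37.6%, or 3.4 points low.
- Reading B (SS denominator, as in 8.1.5 and 8.1.6): 45.9/140 = 32.8%, or 8.2 points low. The 17.9 removed participants (17.9/140 = 12.8%) are then counted neither as free nor as not free.
- Month 12 is unaffected, because participants stay in through the period of the FV: 89.6/140 = 64.0% = S(2).

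**Other shares, same assumptions**

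| Early FV | Followed | Free at Month 24 | Failures kept | Reading A | Reading B |
|---|---|---|---|---|---|
| 0% | 140 | 57.3 | 0 | 41.0% | 41.0% |
| 10% | 126 | 51.6 | 5.0 | 39.4% | 36.9% |
| 20% | 112 | 45.9 | 10.1 | 37.6% | 32.8% |
| 30% | 98 | 40.1 | 15.1 | 35.5% | 28.7% |

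**Wider range.** Spread the FVs equally over the ends of periods 1 to 3, with q from 0.80 to 0.95 and c from 10% to 30%. Reading A is (1 − c)q⁴ / [1 − c + (c/3)Σ(1 − q^j)], j = 1 to 3; reading B is (1 − c)q⁴. Reading A is low by about 1 point (q = 0.95, c = 10%: 80.6% against 81.5%) to 5 points (q = 0.80, c = 30%: 35.6% against 41.0%). Reading B is low by about 4 points (q = 0.80, c = 10%: 36.9% against 41.0%) to 24 points (q = 0.95, c = 30%: 57.0% against 81.5%).

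**Censoring at the FV (c = 20%).** At risk in periods 1 to 4: 140, 112, 71.7 (89.6 free minus 17.9 censored) and 57.3. The share staying free is 0.80 in each, so the estimate is 0.80⁴ = 41.0%.

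**If the FV is related to outcome.** Let r be the probability that someone free at the FV would have stayed free to Month 24. The full-follow-up value is 0.80 × 0.4096 + 0.20 × 0.64 × r = 0.328 + 0.128r. Independence implies r = 0.4096/0.64 = 0.64. Reading A is too low whenever r exceeds 0.376 and too high below that. Reading B is 0.328, so it can never exceed the full-follow-up value.

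**The case against.** Several points on the other side are sound.

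- **Keeping failures is right.** Cumulative freedom requires freedom in all preceding periods, so one failure settles every later period. A reader might infer that retaining failures is itself the bias whatever the denominator. The SAP text does not support that: with the SS denominator, retained failures do not change the seizure-free percentage at all. The whole loss comes from free participants leaving the numerator. The asymmetry acts through the denominator only under reading A.
- **Removing every early-FV participant is not enough.** With the SS denominator it leaves 45.9/140 = 32.8% unchanged, and it discards people whose later status is already known.
- **Other measures of sustained control exist.** A reader might take the cumulative analyses to be the only one. Diary freedom over the whole Evaluation Period to Month 24 is a secondary endpoint (SAP 2.2.2, 3.13.4) that keeps participants with an early FV, and 3.13.9 also assesses consecutive diary freedom over that period.
- **Month 12 is largely spared.** Only an FV in the first six months can affect it.
- **The size is unknown.** Planned participation is at least 2 years unless approval, an access program or the end of development comes first (protocol 4.1). The documents do not say how many FVs will precede Month 24.
- **The endpoints are low in the hierarchy.** Consecutive freedom is listed under other endpoints and no testing is planned (SAP 4.3). The expected bias is downward, so it would not flatter the drug.

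These points limit the importance of the problem. They do not remove the downward bias when the FV is unrelated to outcome, or the conflict between the exclusion rule and the stated denominator.

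**Conclusion.** The concern holds in this form: participants still free at an early FV are dropped rather than censored, and the SS denominator contradicts the exclusion. If the FV is unrelated to outcome, cumulative freedom in periods after the FV is too low under both readings. In the illustration at 20% early FV, the Month 24 value is 37.6% or 32.8% against a true 41.0%. Across the assumed range the shortfall is about 1 to 5 points if excluded participants leave the denominator and about 4 to 24 points with the SS. It is zero without early FVs. The per-period rates, FV shares and FV timing are all assumed.

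Severity is moderate. A reader might infer that the study's main conclusions are at risk. The documents do not support that: the primary objective is safety, these summaries are descriptive, and whole-period diary freedom is reported alongside them.

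**What to change.** - **SAP 3.13.8 and 3.13.9:** censor a participant who is still free at an FV before Month 24 at the end of the last assessed period. For the diary, this is the FV period if the 80% completion criterion is met in it, and otherwise the period before. Estimate cumulative freedom by Kaplan-Meier (life table) over the 6-month periods, with the event being the first period classed as not free. Early discontinuation stays a failure, as now.
- **SAP 8.1.5 and 8.1.6:** base the cumulative percentages on the number at risk instead of the full SS, and show that number for each period.
- **Failure first seen at the FV:** the EEG rule covers failure before the FV, while the diary rule covers failure before or at it. An EEG failure first seen at the FV is therefore not clearly assigned. Use the same wording in both.
- **Reporting:** give the number of FVs before Month 24 by period, split by status at the FV, so that readers can judge the effect.

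The cost is SAP wording and one programming change, with no new data. The downsides are that later periods rest on fewer participants and that Kaplan-Meier assumes the FV is unrelated to outcome, which the SAP should state.

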3.13.9 Consecutive absence seizure freedom based on diary

The endpoint of consecutive absence seizure freedom based on diary is defined, per 6-month period within the Evaluation Period, as having no absence seizures during that period. This will be assessed at 6-month time intervals within the Evaluation Period, as defined in [Table 3-4](#), and over the entire Evaluation Period. Consecutive absence seizure freedom for the Evaluation Period is defined as having no absence seizures for the entire Evaluation Period which also includes any additional diary entries collected from the end of the 6-month Months 19 to 24 period up to the Month 24 YEV where this is truncated for participants who reach the Month 24 YEV.

The endpoint of cumulative consecutive absence seizure freedom is defined, per 6-month period within the Evaluation Period, as having no absence seizures during that period and all preceding periods (where applicable). This will be assessed at 6-month time intervals within the Evaluation Period, as defined in [Table 3-4](#).

The derivation will be the same as that outlined in [Section 3.13.4](#), except without the consideration of concomitant AEDs or benzodiazepines usage.

In each 6-month period (or Evaluation Period), a study participant is defined as absence seizure free if they meet all the following criteria:

1. The study participant completed their seizure diary on at least 80% of days within the relevant period. Seizure diary is defined as completed if “Diary completed” is answered “Yes” for each applicable day in the period. If “Diary completed” is answered “No” or the diary record is missing it will be defined as not completed for that day.
2. No absence seizures are reported in the seizure diaries in the relevant period

Specific algorithmic rules for each of the above criteria are defined as follows:

Criterion 1: Seizure diary data is reported on the Seizure Classification eCRF for at least 80% of the days within the relevant period

Criterion 2: No diary records on the Seizure Classification eCRF within the 6-month period are reported with answer “Yes” to the question “Did Any Absence Seizures occur?”

Note that Criterion 2 will only be assessed if Criterion 1 is met. In each 6-month period (or Evaluation Period), if the study participant does not meet all the criteria for absence seizure freedom they will be regarded as not absence seizure free.

If a study participant discontinues the study during a relevant period then Criterion 1 will be checked and if met, the participant will be assessed for absence seizure freedom in the period of discontinuation. If Criterion 1 is not met, then the status will be imputed as not absence seizure free for that specific period and for all subsequent 6-month periods (where applicable), ending at Months 19 to 24.

If a study participant has a FV during a relevant period then Criterion 1 will be checked and if met, the participant will be assessed for absence seizure freedom in the period of the FV. If Criterion 1 is not met, then the participant will not be included in the analyses for that specific period and for all subsequent 6-month periods (where applicable), ending at Months 19-24.

For the cumulative consecutive absence seizure freedom analysis, a study participant will be categorized as absence seizure free until the 6-month period in which they are first classified as not absence seizure free. After the recurrence of absence seizures, the participant is classified as not absence seizure free regardless of whether they met the criteria for absence seizure freedom in subsequent 6-month periods.

If a participant discontinues early, all subsequent 6-month periods for the participant are considered as not absence seizure free, regardless of their cumulative absence seizure status at the time of the EDV.

If a participant performs a FV before the end of the Month 19-24 period and becomes not absence seizure free at any point prior to or at the FV then the participant will remain in the analyses for subsequent 6-month periods as not absence seizure free. However, if the participant performs a FV before the end of the Month 19-24 period, and they remain absence seizure free until the FV, then they will remain in the analyses until the period of the FV if they met Criterion 1 during the period of the FV, or the period prior if they did not meet Criterion 1 during the period of the FV, and will be excluded from the analyses for all subsequent 6-month periods.

3.13.10 EpiTrack Junior

The EpiTrack Junior is a 15-minute screening tool intended to assess and track the cognitive side effects of AEDs in children with epilepsy. This will be conducted at FEVs, YEVs, EDV or FV (as applicable), and SV for study participants between 6 and 18 years old at the time of assessment. Additionally, Last Assessment will be derived based on the last EpiTrack Junior assessment conducted post EV, for each participant in EP0132. Study participants who become 6 years old after EV will be assessed for all visits they are aged ≥ 6 years.

The EpiTrack Junior at the EV in EP0132 will be taken from the last visit in the N01269 analysis database. This will be applicable only for participants who discontinue early in N01269 and have an EDV assessment, or for participants having an unscheduled assessment after the last visit in N01269 and before or on the date of the EP0132 EV.

The screening tool consists of 6 subtests: interference, numbers, numbers and dots, maze test, verbal fluency, and inverted digit span.

The EpiTrack Junior eCRF will be populated with the raw score (ie, number of seconds for subtests 1-4, number of words for subtest 5 and number of figures in highest successful sequence for subtest 6) for each of the subtests, and the borderline assessment. Results from each subtest raw score will be converted in a score from 1 to 7 points as described in [Table 3-7](#). These conversions are taken from the EpiTrack questionnaire.

Table 3-7: Converting EpiTrack raw values to points

	Points						
Subtest	7	6	5	4	3	2	1
Interference (seconds)	≤ 12	13-22	23-32	33-42	43-52	53-62	≥ 63
Numbers (seconds)	≤ 10	11-25	26-40	41-55	56-70	71-85	≥ 86
Numbers and dots (seconds)	≤ 19	20-45	46-71	72-97	98-123	124-149	≥ 150
Maze Test (seconds)	≤ 11	12-23	24-35	36-47	48-59	60-71	≥ 72
Verbal Fluency (number of words)	≥ 25	18-24	11-17	4-10	0-3		
Inverted Digital Span (number of figures)	≥ 6	5	3-4	2	0		

The total unadjusted EpiTrack Junior score will be calculated as the sum of the 6 subtest scores in points. If a study participant is missing any of the raw scores, then the total unadjusted EpiTrack Junior score will be missing.

The total adjusted EpiTrack Junior score will be referred to as “EpiTrack score” and will be obtained from the total unadjusted EpiTrack Junior score by applying an age correction as presented in [Table 3-8](#) (age correction taken from the EpiTrack form). The age correction will use the participant age at N01269 Baseline for all assessments, if the participant was aged ≥ 6 at N01269 Baseline. For participants aged <6 years at N01269 Baseline the age correction will be based on an age of 6 years from the time the first EpiTrack Junior score is completed in either N01269 or EP0132.

Table 3-8: EpiTrack age corrections

Age	Correction
6 years old	+14
7 years old	+7
8 years old	+4
9 years old	+2
10 years old	None
11-14 years old	-2
15-18 years old	-4

Additionally, if the investigator has ticked the “borderline cases” box at N01269 Baseline, or at the first visit at which the EpiTrack was assessed (investigator may add one more point for “male subjects younger than 13 years old” and for “subjects that do/did not attend any secondary school”) one point will be added when deriving the EpiTrack score at this and at all subsequent time points.

Study participants will be classified into a cognitive performance category based on their EpiTrack score:

- “Good”: ≥ 36 points
- “Average”: 31-35 points
- “Mildly impaired”: 29-30 points
- “Significantly impaired”: ≤ 28 points

The CFB in the EpiTrack score will be calculated by subtracting the N01269 Baseline result from the EV/FEV/YEV/EDV/EV/SV/Last Assessment result. CFB will therefore not be calculated for participants who did not complete the EpiTrack at N01269 Baseline.

Study participants will be classified into categories of change in cognitive function as specified on the EpiTrack form:

- “Improved”: change in score ≥ 3
- “Unchanged”: change in score between -1 to 2
- “Worsened”: change in score ≤ -2

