(Down-Titration Period). A Down-Titration Visit (DTV) will be performed at the end of the Down-Titration Period, and study drug will be discontinued at the DTV. After 2 weeks free of study drug (Safety Period), study participants will complete the SV.

Brivaracetam (tablet and oral solution) will be administered twice per day in equal doses. The maximum allowed daily dose in EP0132 is 200mg/day (4mg/kg/day). Dose adjustments of BRV and/or concomitant AEDs based on clinical judgment are allowed at any time, 3 days after study start and onwards.

The duration of the study per study participant will be 2 years at minimum, until approval of BRV for the indication of CAE or JAE has been obtained for pediatric participants in their age range, until a managed access program is established as allowed per country-specific requirements in addition to legal and regulatory guidelines, or until the investigational product development in the related indication is stopped by the Sponsor, whichever comes first.

This study will be conducted using a site-based model; all study assessments will be conducted at the study site.

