8.1.9 Participant- or caregiver-reported outcomes

The patient- or parent-reported outcomes that will be assessed in this study are summarized in Table 8-1 and described in the following subsections.

Table 8–1: Participant- or caregiver-reported outcomes

| Assessment | Time points assessed | Participant age at assessment ^a |
|--------------------|---|---|
| EpiTrack Junior | FEV, YEV, and EDV or FV (as applicable) | 6 to <18 years |
| PedsQL Core Module | FEV, YEV, and EDV or FV (as applicable) | Participant self-report: 5 to ≤7, 8 to ≤12, and 13 to ≤17 years Parent proxy-report: 2 to ≤4, 5 to ≤7, 8 to ≤12, and 13 to ≤17 years |

EDV=Early Discontinuation Visit; FEV=Full Evaluation Visit; FV=Final Visit; PedsQL=Pediatric Quality of Life;
YEV=Yearly Evaluation Visit

Note: Whole years are considered when determining participant age; ie, a 5-year-old is considered 5 until they turn 6 years old.

^a The version of the assessment test should be in accordance with the study participant's age at the time of the assessment. If the participant has aged into a different version of the assessment test since the initial assessment in N01269, then the same version of the assessment should be completed at the initial assessment in EP0132, and subsequently, the version of the assessment test in accordance with the study participant's age at the time of the assessment should be used.

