8.2.5 Pregnancy

Details of all pregnancies in female participants and female partners of male participants will be collected after the start of study treatment and until 2 days (ie, 5 half-lives) after the last dose of study medication.

If a pregnancy is reported, the Investigator must immediately inform the Sponsor within 24 hours of learning of the pregnancy and should follow the procedures outlined in Appendix 4 (Section 10.4).

Should a participant become pregnant during the study, she should be withdrawn from the study as soon as pregnancy is known (by positive pregnancy test), and the following should be completed:

- The participant should return for an EDV.
- The participant should immediately stop the intake of the study medication or be down-titrated as instructed at the EDV.
- An SV should be scheduled 2 weeks after the participant has discontinued her study medication.

Every reasonable attempt should be made to follow the health of the child for at least 30 days after birth for any significant medical issues. In certain circumstances, UCB may request that follow up is continued for a period up to 12 months. Abnormal pregnancy outcomes (eg, spontaneous abortion, fetal death, stillbirth, congenital anomalies, ectopic pregnancy) are considered SAEs.

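### The EpiTrack Junior Last Assessment takes the off-drug Safety Visit score for participants who stop brivaracetam and are tested there, so one row mixes off-drug and on-drug scores

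*SAP*

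**What the plan says.** On the visits, SAP 3.13.10 states: "This will be conducted at FEVs, YEVs, EDV or FV (as applicable), and SV for study participants" in the stated age range. Protocol 8.1.9.1 gives the same visits, and protocol Table 1-2 marks EpiTrack Junior in the Safety Period column. Protocol Table 8-1 lists the FEV, YEV and EDV or FV for this test, but not the SV.

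On the derived time point, SAP 3.13.10 adds: "Last Assessment will be derived based on the last EpiTrack Junior assessment conducted post EV, for each participant in EP0132". Nothing restricts this to treatment or excludes the SV. Change from baseline is obtained "by subtracting the N01269 Baseline result from the EV/FEV/YEV/EDV/EV/SV/Last Assessment result", so the SV and Last Assessment are separate time points. (The list prints EV twice; the PedsQL counterpart in SAP 3.13.11 has FV in the second position.)

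On the timing of the SV, protocol 4.1 says: "After 2 weeks free of study drug (Safety Period), study participants will complete the SV". The same section exempts from down-titration and the SV anyone who moves to another brivaracetam study, an access program or commercial brivaracetam.

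On reporting, SAP 10.6.1 summarises scores, change from baseline and the change categories by visit. It does not name Last Assessment. SAP 3.3.7 and 3.3.8 assign an EDV or FV score to a scheduled visit only if it falls in that visit's window, and show it there only if the test was planned at that visit.

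**The concern.** The exploratory objective is the long-term effect of brivaracetam on cognition, among other outcomes, and the tool is described as one for following cognitive side effects of antiepileptic drugs. A row called Last Assessment will be read as each child's final status on the drug. Under the SAP rule it is that for some participants. For others it is a score taken after the drug has gone, and the split follows whether the child stopped brivaracetam.

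If brivaracetam lowers performance reversibly, a child who had declined by the EDV and recovered by the SV would be counted in this row as having no decline. The final on-drug score may then have no other clear place in the tables.

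**Working it through.** The plan states no figure on this point, so there is none to reproduce. The check reads the derivation rule against the visit schedule, with some short arithmetic.

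1. **Which score is selected.** The order of visits for a participant who stops is FEV/YEV, then EDV or FV, then the Down-Titration Visit if needed (no EpiTrack), then SV. The last post-EV score is the SV score whenever it is complete. For a participant who continues brivaracetam elsewhere there is no SV, so the last score is the FV score or an earlier one.

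2. **Whether the SV is off drug.** Protocol 4.1 says so directly. As a cross-check, protocol 8.2.5 collects pregnancies "until 2 days (ie, 5 half-lives) after the last dose of study medication". Half-life = 2 days / 5 = 0.4 day. Then 14 / 0.4 = 35 half-lives, and 0.5^35 is about 3 × 10^-11 of the drug. Down-titration can last up to 4 weeks, so the SV can come about 4 + 2 = 6 weeks after the EDV or FV.

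3. **Who is affected.** Participants must stop brivaracetam, attend the SV, be in the age range there, and have all six subtests (SAP 3.13.10 makes the total missing otherwise). They must also not be excluded by SAP 10.6.1, which drops those who turn 6 after N01269 Baseline and those who turn 18 by the first scheduled EP0132 assessment.

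4. **Whether the by-visit tables carry the displaced score.** EpiTrack is planned at 6-monthly visits (Days 183, 365, 548 and 731 in SAP Table 3-5) with windows of ±7 days, that is 15 days each. If EDV dates were spread evenly over time (an assumption), 15 / 183 = 8% of EDV scores could be mapped. A participant who stops before the Month 6 window has only EDV and SV scores, so no FEV or YEV row holds any score for that child.

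5. **Effect on the mean.** Shift = s × d, where s is the share of participants in the row whose score comes from the SV, and d is the off-drug change in points. Neither is in the documents. With assumed s of 10% to 50% and d of 1 to 3 points, the shift runs from 0.10 × 1 = 0.1 to 0.50 × 3 = 1.5 points.

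6. **Effect on the categories** (Worsened is -2 or lower, Unchanged is -1 to 2), with assumed scores:
   - Baseline 32, EDV 30, SV 32: change is -2 (Worsened) at the EDV but 0 (Unchanged) as Last Assessment.
   - Baseline 32, EDV 32, SV 30: change is 0 (Unchanged) at the EDV but -2 (Worsened) as Last Assessment.

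7. **Comparison with PedsQL.** SAP 3.13.11 defines Last Assessment in parallel terms, but PedsQL is not done at the SV, so the same definition does not pick up an SV score there.

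**The case against.** The strongest reply is that Last Assessment is a side product. The stated endpoint is change from baseline to each applicable visit. SAP 10.6.1 reports by visit and never mentions Last Assessment, and the protocol does not define it. The on-drug FEV and YEV scores stay in the tables. An FV inside a window is mapped, so someone who stops at Month 24 keeps an on-drug score in that row. The EDV and SV are already named as change-from-baseline time points, and all scores are listed. This stands, and it limits the weight of the point. It does not remove it: SAP 3.13.10 derives Last Assessment and its change from baseline, and SAP 10.6.1 does not say whether an unmapped EDV score gets a row of its own.

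A reader might infer that everyone who stops brivaracetam is affected. The documents do not support that. SAP 3.3.5 foresees missed SVs, and incomplete tests and the age exclusions remove others.

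A reader might also infer a bias towards showing no cognitive harm. That needs two things the documents do not give: that children with cognitive side effects stop more often, and that scores recover off drug. Seizure recurrence, or another antiepileptic drug started by then, could lower the SV score. The protocol itself notes a negative effect of valproate on attention. Such a shift would be equally misleading in a row about brivaracetam, but it means the direction is open.

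Finally, an EDV or FV score is not always strictly on drug, since SAP 3.13.12 and 4.1.4.5 allow for a last dose before those dates. That is fair, and it bears on how the fix is worded.

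**Conclusion.** The point holds for participants who stop brivaracetam, complete EpiTrack Junior at the SV and are eligible for the summaries. For them Last Assessment is an off-drug score that displaces the EDV or FV score, while participants who continue on other brivaracetam supply cannot contribute an SV score. The row therefore mixes exposure states by stopping status. It is not the whole summary of the drug's effect on cognition, because the FEV and YEV rows are untouched. It may, however, be the clearest summary available for a final EDV or FV score that falls outside a visit window.

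The number affected, the size of the shift and its direction cannot be computed from the documents. The range of 0.1 to 1.5 points and the 8% mapping figure rest on the assumptions stated with them. A reversible on-drug decline would be hidden in this row; recurrence or a new drug could move it the other way. Because the endpoint is exploratory, descriptive and untested, the severity is minor to moderate.

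**What to change.** In SAP 3.13.10, define the EpiTrack Junior Last Assessment as the last post-EV score up to and including the EDV or FV. Report the SV only as its own time point, labelled as off drug; that row then also shows whether any change reverses. If a strictly on-drug value is wanted, add a condition on the date of last dose, because the visit-based rule does not guarantee it. In SAP 10.6.1, say whether Last Assessment and unmapped EDV or FV scores are tabulated. Reconcile protocol Table 8-1 with protocol 8.1.9.1 and Table 1-2 on whether the test is done at the SV.

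The core change costs one sentence and one derivation, and needs no new data. The SAP 10.6.1 clarification is a further sentence, and the protocol inconsistency is a text correction.
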